12.1.2 Drug-Related Adverse Events

All TEAEs assessed by investigator as study drug related (ADR) will be summarized by SOC, PT and severity for each dose cohort and overall.

12.1.3 Deaths and Serious Adverse Events

Serious adverse events and SAEs assessed by investigator as study drug related (serious ADR) will be summarized by SOC, PT and severity for each dose cohort and overall. A list of subjects who died and all SAEs will be provided.

12.1.4 Adverse Events Causing Early Discontinuation

Adverse events that cause early discontinuation of study will be summarized by SOC, PT and severity for each dose cohort and overall if needed. In addition, a list of subjects with the AEs resulting in discontinuation of study will be provided.

12.1.5 Events of Interest

The following events of interest, which include EOSI defined in the protocol, will be summarized by PT, if applicable. A list of subjects will be provided for each type of EOSI. AE profile summary including time

Proprietary and Confidential Pg. 21 of 38

to event onset from infusion and duration of the events will be generated for EOSI (unless otherwise specified below).

Transaminitis

- ALT elevation reported as EOSIs (Preferred term: "Alanine aminotransferase increased", reported as EOSI).
- AEs of liver dysfunction, defined using the MedDRA search strategy high level term (HLT = "Liver function analyses").
- o Potential Hy's law cases
 - ALT or AST $\ge 3x$ ULN and serum TBL $\ge 2x$ ULN
 - Assessments of ALT/AST and TBL must be on the same day

A listing will be provided.

- Infusion related reaction, Hypersensitivity, Anaphylactic or Anaphylactic reactions
 - o Infusion related reactions, defined as AEs occurring during BMN 270 infusion or within 48 hours post-infusion, will be summarized as follows:
 - Subjects who receive infusion with initial rate of approximately 4 mL/min
 - The rest of the subjects, i.e. subjects who receive infusion with initial rate of 1 mL/min
 - All treated subjects
 - Systemic hypersensitivity (Hypersensitivity [SMQ] narrow scope).
 - Anaphylactic, or anaphylactoid reactions (Anaphylactic reaction [SMQ] algorithmic) listing only.
- Thromboembolic events:
 - o Embolic and thrombotic events (SMQ) for entire study period.
 - AEs suggestive of thromboembolic events: for subjects who have FVIII elevation > 150% any time during study, a listing of clinical terms suggestive of thromboembolic events observed from the time point prior to when FVIII was elevated until FVIII falls below 150%. (The preferred terms are listed in Appendix 17.2.)
- Development of anti-FVIII Inhibitors as measured by Nijmegen modified Bethesda Assay (Preferred term: "Anti factor VIII antibody positive")

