12.2 Clinical Laboratory Tests

Clinical laboratory tests include blood chemistry, haematology, urine tests, CRP and coagulation. Clinical laboratory test values and change from Baseline will be summarized descriptively by visit for each dose cohort and overall. Shift tables cross-tabulating CTCAE v4.03 grade at Baseline vs. worst CTCAE v4.03

Proprietary and Confidential Pg. 22 of 38

grade at post-Baseline visits will be provided as well. A supportive listing of abnormal test values with CTCAE v4.03 grade 3 or greater will be produced.

Liver tests (LTs) by central labs will be assessed on a regular basis, as detailed in the protocol. Boxplots of maximum ALT values at 4-week intervals over time and corresponding line plots will be provided by cohort. The same analyses based on mean or median ALT values may be conducted. ALT values and change from Baseline over time will be summarized descriptively by dose cohort. Summaries of ALT elevations including baseline ALT, time from infusion to ALT > ULN, ALT > 3x ULN, ALT > 5x ULN, ALT $\geq 1.5x$ ULN or (> ULN & > 2x baseline value), peak ALT level, duration of ALT elevation will be provided. Correlation of ALT elevation to FVIII levels, as well correlation of steroid treatment to ALT elevation and FVIII levels will be examined using subjects' profile figures. Local ALT assessments will be analyzed similarly as the central ALT assessments, if needed. Similar analyses will be applied to other liver tests including aspartate transaminase (AST), gamma-glutamyl transferase (GGT), lactate dehydrogenase (LDH), bilirubin, and alkaline phosphatase (ALP), if needed.

In addition, incidence of potential drug-induced liver injury (DILI) that include an elevated ALT or AST in combination with either an elevated bilirubin or clinical jaundice, as defined by Hy's law, will be summarized by count and percentage. The profile summary of the related laboratory tests results needed for determination by Hy's law will be provided for the subjects with potential DILI.

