17.2 Preferred terms suggestive of thromboembolic events

confusional state (10010305)

muscular weakness (10028372)

swelling (100426740)

peripheral swelling-10030124)

odema Peripheral (10048959)

jaundice (10023126)

urine output decreased (10059895)

pain in extremity (10033425)

erythema (10015150)

dyspnea (10013968)

chest pain (10008479)

chest discomfort (10008469)

tachycardia (10043071)

haemoptysis (10018964)

presyncope (10026653)

headache (10019211)

hypoaesthesia (10020937)

eye pain (10015958)

eye swelling (10015967)

visual impairment (10047571)

visual acuity reduced (10047531)

Proprietary and Confidential

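### The event of interest labelled as liver dysfunction is retrieved only through a liver-test high level term, so a liver AE coded only to a clinical term falls outside it

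*SAP*

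**What the plan says.** Section 12.1.5 places three liver items under the heading 'Transaminitis':

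1. "ALT elevation reported as EOSIs (Preferred term: 'Alanine aminotransferase increased', reported as EOSI".
2. "AEs of liver dysfunction, defined using the MedDRA search strategy high level term (HLT = 'Liver function analyses".
3. Potential Hy's law cases: ALT or AST at least 3 times ULN with total bilirubin (TBL) at least 2 times ULN, and "Assessments of ALT/AST and TBL must be on the same day".

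The section summarises its events of interest by preferred term. For events of special interest (EOSI) it adds a subject list and a profile of time to onset and duration.

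Other topics in the section are searched by SMQ, for example "Systemic hypersensitivity (Hypersensitivity [SMQ] narrow scope" and "Embolic and thrombotic events (SMQ) for entire study period". Anaphylactic reactions also use an SMQ.

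Section 12.2 separately summarises potential drug-induced liver injury, meaning raised ALT or AST "in combination with either an elevated bilirubin or clinical jaundice, as defined by Hy's law".

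**The concern.** The label of the second item is wider than its search. A reader of a table of liver dysfunction AEs will expect clinical diagnoses and signs as well as abnormal test results. The rule names one high level term, whose title refers to analyses. No SMQ, system organ class or clinical hepatic preferred term is added.

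This matters because the vector is designed to act in the liver: Section 2.1 describes a liver-selective promoter and synthesis of FVIII from transduced liver tissue. Laboratory findings are already covered in several places, namely the ALT summaries in Section 12.2 and a separate listing of AEs in the Investigations system organ class in Section 12.1.1. Clinically worded liver AEs have no targeted grouping of their own. With so few subjects, one person in or out of the grouped count is visible.

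**Working it through.** The plan gives no figure to reproduce on this point. The check takes each place where a clinical liver AE could be picked up and asks what selects it.

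**Liver items in Section 12.1.5**

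| Item | Selected by | Selects an AE coded only to a clinical liver term? |
|---|---|---|
| ALT elevation reported as EOSI | one laboratory preferred term | No |
| AEs of liver dysfunction | one high level term named for liver tests | No, judging by its name |
| Potential Hy's law cases | same-day ALT/AST and TBL values | No; it selects on values, not on AE terms |

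So 3 of 3 items are laboratory-based, and 0 of 3 select on a clinical AE term.

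**Other routes in the SAP**

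- Section 12.1.1: all TEAEs by system organ class, preferred term and severity, plus a TEAE listing.
- Sections 12.1.2 and 12.1.4: drug-related AEs, and AEs causing discontinuation.
- Section 12.1.3: SAEs tabulated and listed.
- Section 12.2: clinical jaundice enters the drug-induced liver injury summary, but only together with raised ALT or AST.
- Appendix 17.2: "jaundice (10023126") is on the list of terms suggestive of thromboembolic events. Section 12.1.5 uses that list only for subjects whose FVIII exceeds 150%, and only around that elevation. It is not a liver search.

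The event is therefore reported somewhere, but not under the liver event of interest.

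**Size**

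Inputs: up to 15 subjects dosed (Section 2.5); 3 subjects in Cohort 4, with 3 more possible (Section 2.2). The SAP gives no count of clinical liver AEs, so this is the effect of one subject on a per-subject incidence. Omitting a subject from n treated lowers the incidence by 1/n if that subject has no other retrieved liver AE, and by 0 otherwise.

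- Overall, n = 15: 1/15 = 6.7 percentage points, or 0.
- Cohort 4, n = 6: 1/6 = 17 points, or 0.
- Cohort 4, n = 3: 1/3 = 33 points, or 0.

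**Potential Hy's law, side by side**

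- Section 12.1.5: TBL at least 2 times ULN, on the same day as the ALT or AST value. Clinical jaundice is not mentioned.
- Section 12.2: raised ALT or AST "in combination with either an elevated bilirubin or clinical jaundice", attributed to Hy's law. No same-day condition is given.

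A subject with raised ALT and clinical jaundice, but no same-day TBL at the threshold, is a case under Section 12.2 and not under Section 12.1.5.

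**The case against.** The strongest reply is that the narrow search may be deliberate. The heading is 'Transaminitis', not hepatotoxicity. Section 12.1.5 says its list includes the EOSI defined in the protocol, which is not at hand, and the SAP's change summary says version 3.0 was revised for the definition of EOSI. A high level term can suit a laboratory topic, and the use of SMQs for other topics does not make it wrong here. The study is small and descriptive, and no formal safety test is planned. This stands in part: it lowers the weight of the point, but it leaves a label that does not match its search.

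Four stronger readings are tempting and are not supported:

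- A reader might infer that clinical liver AEs would appear only in the general tables. Sections 12.1.2 to 12.1.4 and the liver injury summary in Section 12.2 give further routes.
- A reader might infer that the omission falls on the most serious cases, because these tend to be reported as diagnoses. The SAP says nothing about this tendency, and any serious hepatic event is listed under Section 12.1.3.
- A reader might infer that the search merely repeats the ALT item. The SAP does not list the content of the high level term, and its name covers liver tests generally, so it may retrieve more than ALT terms.
- A reader might take the jaundice entry in Appendix 17.2 as a contradiction about liver scope. That list serves a separate thromboembolic listing.

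**Conclusion.** The point holds as a mismatch between label and search. As written, a liver AE coded only to a clinical term gets no liver event-of-interest count, subject list or onset and duration profile, though it is still reported elsewhere. For one such subject the overall incidence is 6.7 points too low with 15 dosed, and unchanged if the subject also has a retrieved liver-test AE.

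This rests on three assumptions. The high level term contains only liver-test terms, which is inferred from its name. The list and profile promised for EOSI are meant to apply to this item. A subject-level incidence is reported for the group.

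The primary efficacy analysis is not affected. The difference between the two potential Hy's law definitions can be read directly from the text and needs none of these assumptions.

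**What to change.** In Section 12.1.5, keep the high level term and add a hepatic SMQ or a named list of clinical hepatic preferred terms. Report laboratory terms and clinical terms on separate lines, each with a subject count, time to onset and duration. Confirm the content of the high level term in the MedDRA version used and state that version. If the protocol intends a laboratory-only topic, rename the item as liver-test AEs instead.

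Reconcile the potential Hy's law definition in Section 12.1.5 with that in Section 12.2, so that the listing and the count are built on one stated rule.

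The cost is a line or two of SAP text and a small programming change. The downside is that a few non-specific hepatic terms may be retrieved and appear in the listing; separate lines keep them from blurring the laboratory count.

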12.1 Adverse Events

Only treatment-emergent adverse events (TEAEs) occurring and reported during the study period will be included in the adverse event summaries. A TEAE is defined as any AE that newly appeared, increased in frequency, or worsened in severity following initiation of study drug administration. Adverse events will be coded in accordance with Medical Dictionary for Regulatory Activities (MedDRA).

An adverse drug reaction (ADR) is any AE for which there is a reasonable possibility that the study drug caused the AE. The investigator will assess the causality for individual AEs, applying the guidance specified in protocol, and those assessed as study drug-related will be considered ADRs.

A serious adverse event (SAE) is any untoward medical occurrence that at any dose meets one or more of the seriousness criteria enumerated in the protocol. AE severity, not equivalent to seriousness, will be assessed using the protocol defined categories using the NCI CTCAE v4.03.

All bleeding events and suspected bleeding events, regardless of the need for exogenous FVIII therapy as treatment, should be captured in subject diaries and recorded on the designated bleeding eCRF. Bleeding

Proprietary and Confidential Pg. 20 of 38

events and suspected bleeding events should not be reported as adverse events, with the following exception:

 All bleeding events and suspected bleeding events which meet one or more of the criteria for being serious (refer to protocol Section 10.2) should be reported as serious adverse events (whether or not they are bleeding events that are normal sequelae of haemophilia, and whether or not they required exogenous FVIII as treatment).

The study AE reporting period is as follows: After informed consent but prior to initiation of study treatment, only SAEs associated with any protocol-imposed interventions will be reported. After informed consent is obtained and the administration of study drug, the reporting period for all non-serious AEs and SAEs begins and continues for approximately 5 years or until study discontinuation/termination, whichever is later.

The following types of AEs will be summarized: all AEs, AEs assessed by investigator as related, SAEs, SAEs assessed by investigator as related, AEs leading to study discontinuation, deaths, EOSIs. Listings will be provided.

If the onset date or end date of an AE is partial, the same imputation rules described in Section 3.5will be applied.

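### The symptom-level thromboembolism listing reads adverse events only, so a non-serious event recorded as a bleed or suspected bleed during FVIII above 150% would not be shown in it

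*SAP*

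**What the plan says.** Section 12.1.5 has two thromboembolic displays. One is an SMQ search over the whole study. The other is at symptom level and is headed as AEs: "for subjects who have FVIII elevation > 150% any time during study, a listing of clinical terms suggestive of thromboembolic events". It runs from the time point before FVIII rose until FVIII falls below 150%. On selection, "The preferred terms are listed in Appendix 17.2". That appendix includes haemoptysis, swelling, peripheral swelling, peripheral oedema and pain in extremity.

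Section 12.1 governs what becomes an AE. It has all bleeds and suspected bleeds, whether or not FVIII was needed, captured in the diary and on a designated bleeding eCRF, and says that bleeding "events and suspected bleeding events should not be reported as adverse events". It gives one exception: events meeting a seriousness criterion are reported as SAEs.

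Section 11.2 sorts FVIII use into categories. One is treatment for adverse events, and it covers bleeds and related symptoms that a person without haemophilia would also have. Another is treatment for bleeding episodes that are normal for haemophilia and are not to be handled as AEs.

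**The concern.** A symptom-level listing is useful for possible thrombosis that nobody diagnosed. Some of the symptoms it looks for can also be read as bleeding, and in this population that is a natural reading. Once a non-serious symptom is recorded as a suspected bleed, Section 12.1 removes it from the only data source that the listing names.

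The interval makes this more relevant. Section 11.2.1 itself says that higher FVIII activity goes with fewer bleeds, so a suspected bleed recorded while FVIII is above 150% is a record that someone looking for thrombosis would want to see. Section 2.5 allows at most 15 subjects to be dosed, so a single event left out can matter to the reading of the display.

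**Working it through.** The plan gives no figure to reproduce and no formula applies. The check sets the sections side by side and counts terms.

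1. **Source of the listing (Section 12.1.5).** It is headed as AEs and selected by preferred term. Section 12.1 describes MedDRA coding of adverse events. No text describes coding of bleeding-eCRF records or adds them to the listing.

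2. **Routing (Section 12.1).** Bleeds and suspected bleeds go to the bleeding eCRF. Only serious ones are also AE records. The rule covers suspected events, so a symptom wrongly attributed to bleeding is routed in the same way as a true bleed.

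3. **Terms affected (Appendix 17.2).** The appendix has 21 terms. Haemoptysis is itself bleeding (entry beginning "haemoptysis (10018964"). Four more could be recorded as a suspected limb or soft-tissue bleed: swelling, peripheral swelling, peripheral oedema, and pain in extremity (entry beginning "pain in extremity (10033425"). That is 1 + 4 = 5 terms, and 5/21 = 24%. Choosing the four is a judgement, and the percentage describes the term list only.

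4. **Where each kind of event would be shown.**

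| Event during FVIII > 150% | Where it would be shown |
|---|---|
| Serious bleed or suspected bleed | SAE list (12.1.3); this listing if the term matches |
| Limb pain or swelling not judged a bleed | Ordinary AE; in this listing |
| Thromboembolic event diagnosed and reported as an AE | SMQ search (12.1.5) |
| Non-serious bleed treated with FVIII | Not in this listing under 12.1; in the profile plots (11.1.1) and the bleeding-episode scatter plots (11.2) |
| Non-serious suspected bleed, untreated | No stated display |

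The last row follows because Section 11.2 defines a bleeding episode as one that needed FVIII replacement. Displays built on that definition leave out an untreated event, although Section 12.1 requires it to be recorded.

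5. **Consistency of the routing rule.** Section 12.1 has one exception, seriousness. The Section 11.2 category of FVIII use for adverse events presupposes a second class of bleeds that are AEs. The two do not agree. If the Section 11.2 view governs, a non-serious haemoptysis might be an AE and would be listed.

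6. **Term codes.** Twenty of the 21 codes have eight digits. The entry "swelling (100426740" has nine.

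**The case against.** The strongest reply is that the listing does what its heading says: it lists AEs, in a descriptive safety section without formal testing, and other displays surround it. The SMQ search covers all subjects for the whole study. There is a full TEAE listing and a list of all SAEs. The profile plots put each subject's FVIII activity on the same time axis as bleeding episodes and FVIII use, and with at most 15 subjects they can be read one by one. Most of this stands, and it is why the gap is narrow. It does not cover the untreated suspected bleed. The plan to repeat the ABR analyses for treated bleeds might suggest that the first set is wider, but the definition given for that set still requires FVIII treatment.

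A reader might infer that haemoptysis and limb symptoms can never appear in the listing. The SAP does not support that. Serious events are reported as SAEs, limb symptoms not judged a bleed remain AEs, and the Section 11.2 category leaves open that some non-serious bleeds are AEs. The Section 11.2 wording on symptoms of a developing bleed does not settle the routing either, because it defines the episode counted for ABR and is tied to FVIII treatment.

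A reader might also take 24% as the share of events lost. It is a count of terms. The SAP gives nothing on how often subjects or sites would class such symptoms as suspected bleeds, and where a bleed is unlikely that label may be used less.

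Finally, a reader might infer from the nine-digit code that a search for swelling would return nothing. Section 12.1.5 selects by preferred term and states no search by code, and the term name is clear. This is a clerical slip.

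**Conclusion.** The point holds in a limited form. Under Section 12.1, the Section 12.1.5 listing would not show a non-serious haemoptysis, or limb pain or swelling classed as a suspected bleed, while FVIII is above 150%. What no stated display covers is the non-serious, untreated suspected bleed in that interval which was not later diagnosed and reported as a thromboembolic event. Its frequency is unknown and cannot be estimated from the SAP.

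This rests on two assumptions: that Section 12.1 governs AE reporting where it differs from Section 11.2, and that bleeding-eCRF records are not coded to preferred terms and merged with the AE data, since the SAP does not say that they are. It is a cheap improvement to one safety listing. It does not show that the plan's thromboembolic surveillance as a whole fails.

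**What to change.** In Section 12.1.5, for the same subjects and the same FVIII > 150% interval, list every bleeding-eCRF record beside the Appendix 17.2 AE terms, whether or not it was treated and whether it was a bleed or a suspected bleed.

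Reconcile the Section 11.2 category of FVIII use for adverse events with the single exception in Section 12.1, so that it is clear which bleeds have an AE record.

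Correct the code printed for swelling in Appendix 17.2 as a clerical matter.

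The cost is one more source dataset in a listing already planned, and a slightly longer listing. Section 12.1 already requires these events to be recorded, so no new collection is needed.

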12.2 Clinical Laboratory Tests

Clinical laboratory tests include blood chemistry, haematology, urine tests, CRP and coagulation. Clinical laboratory test values and change from Baseline will be summarized descriptively by visit for each dose cohort and overall. Shift tables cross-tabulating CTCAE v4.03 grade at Baseline vs. worst CTCAE v4.03

Proprietary and Confidential Pg. 22 of 38

grade at post-Baseline visits will be provided as well. A supportive listing of abnormal test values with CTCAE v4.03 grade 3 or greater will be produced.

Liver tests (LTs) by central labs will be assessed on a regular basis, as detailed in the protocol. Boxplots of maximum ALT values at 4-week intervals over time and corresponding line plots will be provided by cohort. The same analyses based on mean or median ALT values may be conducted. ALT values and change from Baseline over time will be summarized descriptively by dose cohort. Summaries of ALT elevations including baseline ALT, time from infusion to ALT > ULN, ALT > 3x ULN, ALT > 5x ULN, ALT $\geq 1.5x$ ULN or (> ULN & > 2x baseline value), peak ALT level, duration of ALT elevation will be provided. Correlation of ALT elevation to FVIII levels, as well correlation of steroid treatment to ALT elevation and FVIII levels will be examined using subjects' profile figures. Local ALT assessments will be analyzed similarly as the central ALT assessments, if needed. Similar analyses will be applied to other liver tests including aspartate transaminase (AST), gamma-glutamyl transferase (GGT), lactate dehydrogenase (LDH), bilirubin, and alkaline phosphatase (ALP), if needed.

In addition, incidence of potential drug-induced liver injury (DILI) that include an elevated ALT or AST in combination with either an elevated bilirubin or clinical jaundice, as defined by Hy's law, will be summarized by count and percentage. The profile summary of the related laboratory tests results needed for determination by Hy's law will be provided for the subjects with potential DILI.

